## **PROTOCOL**

### **ISMMS GCO 15-1545**

#### **The Impact of Medicaid Health Homes on patients with diabetes**

**8/17/2020**

#### **1) Objectives**

We plan to examine the effects of New York State's (NYS) Medicaid Health Home (HHs) program (a population-targeted intervention at the state level) on the process of care, outcomes, and racial/ethnic disparities among low-income residents of New York City (NYC) with Type II diabetes mellitus. In 2012, NYS Medicaid initiated HHs with the "triple aim" of 1) improving quality, 2) improving outcomes, and 3) reducing costs of care for high-need patients with chronic diseases. The program was designed to enhance care and outcomes for patients with two or more chronic conditions, such as diabetes and coronary disease, HIV, and/or a serious mental health condition. HHs provide these patients with coordination of care, by promoting collaboration among health care providers, social service agencies, community-based organizations, and health insurance plans. Taken together, the roll-out, timing, scope of the program, which currently serves over 60,000 patients in NYC, and the availability of both Medicaid data and unique clinical data in NYC through the NYC-Clinical Data Research Network and the Health Evaluation and Analytics Lab provides an opportunity to evaluate the impact of HHs on diabetes management, complications, and health disparities, using quasi-experimental methods.

Similar care management programs have been shown, in studies of limited scope, to improve intermediate outcomes for patients with diabetes. However, the impact of HHs on processes of care and outcomes among low-income patients with diabetes mellitus in large, diverse, and complex urban settings remains largely unexplored. Additionally, current research on the impact of HHs, both in NYS and elsewhere, does not incorporate individual-level clinical data on chronic disease management. As a result, whether the Medicaid HHs program has impacted the health of patients with diabetes has not been examined. It is also not known how interventions of this scope will affect long-standing racial and ethnic disparities in the quality of care and outcomes of individuals with diabetes. Since similar programs are being implemented nationally, it now is critically important to evaluate the effects of HHs on the process and outcomes among patients with diabetes, a condition with multiple complications, which are disproportionately prevalent among racial and ethnic minorities and low-income populations in the United States.

We plan to use two complementary sources of longitudinal individual-level data: 1) NYS Medicaid administrative and claims data and 2) the New York City-Clinical Data Research Network (NYC-CDRN), funded by the Patient-Centered Outcomes Research Institute (PCORI). The NYC-CDRN has identified a cohort of patients with diabetes (approximately 90,700 Medicaid enrollees with diabetes) from 7 large health systems based on electronic health record data; and it has developed a common data model that includes clinical variables related to the process and outcomes of care of patients with diabetes. Using information available from the two complementary data sources and quasi-experimental methods, we will assess the impact of Medicaid HHs in NYC.

Among adult Medicaid patients with diabetes in NYC, we propose:

**Aim 1:** To assess the impact of HHs on the process of care for patients with diabetes.

**Aim 2:** To assess the impact of HHs on the health outcomes of patients with diabetes.

**Aim 3:** To assess the impact of HHs on racial and ethnic disparities in the process of care and outcomes among Medicaid patients with diabetes.

Our sample will include Medicaid enrollees with diabetes who are seen at NYC-CDRN sites and in HHs (estimated 6,500-20,000) and a matched comparison group of Medicaid enrollees with diabetes who are part of the NYC-CDRN, but not HHs. We plan to develop a set of propensity score matched controls, based on a set of patient, practice, and market-level (zip-code) characteristics. We will use quasi-experimental methods to investigate the magnitude of the effects of the HHs program between 2010 and 2017. This secondary data analysis is referred to as **Activity 1** in this protocol. In addition, we will gather information regarding the patient experience of HHs through interviews (**Activity 2**). We will also utilize interviews with HH leaders and care managers from NYC HHs to further characterize these entities (**Activity 3**). Columbia University will participate in only **Activity 1**.

8/20/20 update: Apart from evaluating the impact of the NYS Medicaid HH program on the process and outcomes of care for low-income NYC residents with diabetes, compared to non-enrolled residents with similar conditions and utilization histories, we have received funding to extend this work to examine the impacts of the COVID-19 pandemic on this vulnerable population, a majority of which is Black or Latinx. We hypothesize that HH participation will reduce pandemic-related disruptions in access to health care and social services and improve health outcomes among patients with diabetes in NYC. Using a quasi-experimental difference-in-differences design, we will contrast access and utilization of health care and social services and health outcomes among HH enrollees and non-enrollees during a baseline period prior to the pandemic (CY2019) with each month of the pandemic time period (2020).

**Aim 4:** Using Medicaid claims data, we will estimate the impact of HH enrollment compared to usual care among Medicaid-insured patients with diabetes and other chronic conditions on access to health care and social services and COVID-19 and non-COVID-19 clinical outcomes, as well as racial/ethnic disparities in these outcomes, before and during the pandemic in NYC.

Using Medicaid claims only, we will identify HH participants with diabetes living in NYC in 2019, and use matching and weighting methods to develop a non-HH comparison group who were similar to HH enrollees in their demographics, comorbidities and utilization histories. We will then conduct difference-in-differences analyses using an “event study” framework to compare the pre-COVID time period (CY2019) to each month of the post-COVID period (2020) in terms of access, utilization, and clinical outcomes between the HH and matched non-HH group, overall and stratified by race/ethnicity (Activity 4).

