The identification of individuals eligible for HHs is initiated by one of two processes: a NYS Department of Health (DOH) predictive algorithm utilizing Medicaid services data, which prioritizes individuals based on risk of future hospitalization; and community or “bottom up” referrals from healthcare providers, community-based care management providers, including harm reduction providers, and other agencies such as those who serve individuals re-entering the community from jail or prison. Enrollment in HHs has been slower than expected, and several challenges have been identified and are being addressed by the NYS DOH. These include inaccuracies in the lists of targeted individuals, challenges in the recruitment process, and individuals electing not to participate in the program.(16) The new program may put stress on already under-resourced facilities, by increasing the complexity of billing, the requirements around health information technology (HIT), the caseloads of facilities and case managers, and, in some cases, lowering reimbursement for care management services. Another significant change brought about by HHs is the expanded scope of health conditions of clients served by care management agencies that formerly provided case management for people living with HIV/AIDS, substance use disorders, or serious mental illness ([name], personal communication, March 9, 2015).

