2) In order to be eligible for the cohort, subjects need to have been insured by Medicaid at some point during the years 2010-2016. This categorization will be available in the NYC-CDRN data set. Data will be gathered only from individuals who meet criteria for diabetes and have been insured by Medicaid.

3) Subjects who have participated in the HH program will be the treatment group in this study. Medicaid data contains a field that will identify those patients who were a part of this program during the study period. Our comparison group will consist of similar individuals who were not part of the HH program. The comparison group will be constructed of patients who have been propensity score matched to those in the treatment group, and are therefore similar on a number of characteristics.

**Activity 2:** For the focus group and interview aspect of this study, we will be conducting 2 rounds of data collection, in years 2 and 5. We aim to recruit 20-40 participants in year 5. Year 5 data collection will consist of only individual interviews. Inclusion criteria are as follows:

- a. English-speaking
- b. Are enrolled in a HH
- c. 18 years old or older

All participants must be able to provide informed consent to participate, and must be able to speak with a study staff member over the phone/video call. All individuals must be able to communicate in English.

The ISMMS study team will coordinate with stakeholders who lead NYC HHs to engage HH members/patients who are potential participants.

**Activity 3: HH leaders:** In order to participate in this portion of the study, individuals must speak English and be in a leadership position at a HH entity in NYC or a NYC HH-affiliated Care Management Agency (CMA). Other than not meeting the inclusion criteria, there are no exclusion criteria.

**Care managers:** In order to participate in this portion of the study, individuals must speak English and be in care manager position with a NYC HH-affiliated Care Management Agency (CMA). Other than not meeting the inclusion criteria, there are no exclusion criteria.

**Activity 4:** For this analysis, the study cohort will consist of patients who: 1) have Type II diabetes, 2) are insured by Medicaid, and 3) are either part of a Health Home or meet criteria for Health Home enrollment, but are not enrolled in a Health Home. These criteria will be determined using only Medicaid claims data.

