**2) Health home indicators and patient co-morbidities**

Indicators available include whether the individual was enrolled in the HH program, the date of joining the program, the name/location of the HH, patient-level co-morbidities and chronic conditions (additional diagnoses).

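### Aim 4 does not require Health Home enrolment to precede its 2019 baseline, so the effect of joining during 2019 can be read as pandemic protection

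*Protocol*

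**What the plan says.** The 8/20/20 update in section 1 (Objectives) adds Aim 4 and its analysis, Activity 4. Its hypothesis is that "HH participation will reduce pandemic-related disruptions in access to health care and social services". For the exposed group, "we will identify HH participants with diabetes living in NYC in 2019". Comparison patients are to be found by matching and weighting so that they are "similar to HH enrollees in their demographics, comorbidities and utilization histories". The event-study analysis will then "compare the pre-COVID time period (CY2019) to each month of the post-COVID period (2020"). The paragraph introducing the update gives the same two periods.

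Section 5b (Inclusion and Exclusion Criteria) limits Activity 4 to Medicaid patients with Type II diabetes who "are either part of a Health Home or meet criteria for Health Home enrollment, but are not enrolled in a Health Home". It attaches no date to that status. Section 5e, item 2, lists among the available indicators "whether the individual was enrolled in the HH program, the date of joining the program". No section uses the joining date to set the Aim 4 group or its baseline.

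**The concern.** The hypothesis is about buffering: whether people in an HH lost less care during the pandemic than similar people outside one. To isolate that, HH status should be constant across the baseline, so that the change into 2020 reflects the pandemic and not a change of status. The same calendar year both identifies the group and supplies the baseline, so status may change inside the baseline. A patient who joins at the start of November 2019 contributes ten unexposed baseline months and then a fully exposed 2020. That patient's change contains the effect of starting in an HH, which would have appeared without any pandemic.

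A second route to bias comes from how people are enrolled. The Background section on Medicaid Health Homes says that the state's algorithm "prioritizes individuals based on risk of future hospitalization". If utilization tends to be high just before joining, the baseline of 2019 joiners is raised, and its later fall could also look like protection against hospital use.

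At stake is the interpretation of the Aim 4 estimate. Even with no buffering at all, a difference between the groups could appear and be credited to HHs as a pandemic effect.

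**Working it through.** **Inputs.** From the protocol: group identified by 2019, baseline calendar year 2019, follow-up each month of 2020, no condition on when enrolment began. The protocol states no joining rate, leaving rate or effect size for Aim 4, so there is no figure to reproduce. The shares below are assumptions.

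**Notation.** d = ordinary effect of being in an HH while enrolled; b = additional effect of being in an HH during the pandemic (buffering); j = share of the HH group that joined evenly through 2019; q = share no longer enrolled in a given month of 2020. Effects are taken as additive and immediate on joining, and the groups as otherwise following parallel trends.

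**Step 1: nobody leaves (q = 0).**
- Enrolled share of HH-group time in 2019: 1 - j/2, because even joiners are unexposed for half the year on average.
- HH minus comparison in 2019: (1 - j/2)d. In 2020: d + b.
- Difference-in-differences: (d + b) - (1 - j/2)d = b + (j/2)d.

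| j | Baseline time enrolled | Expected estimate |
|---|---|---|
| 0 | 1.00 | b |
| 0.2 | 0.90 | b + 0.10d |
| 0.3 | 0.85 | b + 0.15d |
| 0.4 | 0.80 | b + 0.20d |

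**Step 2: the monthly event study.** The enrolled share in month m of 2019 is 1 - j + j(m - 0.5)/12. With j = 0.2:
- January: 0.80 + 0.20 × 0.5/12 = 0.808.
- December: 0.80 + 0.20 × 11.5/12 = 0.992.

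The 2019 months would therefore carry a trend that comes from enrolment and not from the pandemic. Plotting by month displays the problem but does not remove it.

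**Step 3: people who leave.** With leavers kept in the HH group, the 2020 difference is (1 - q)(d + b), and the estimate becomes (1 - q)(d + b) - (1 - j/2)d = (j/2 - q)d + (1 - q)b. If enrolment precedes the baseline (j = 0) and q = 0.2, this is 0.80b - 0.20d. Fixing the group before the baseline removes the joiner term. The leaver term remains and has to be described as part of the estimand.

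**The case against.** The strongest reply is that the protocol is brief here and does not decide the point. The words about 2019 could date residence in the city and not participation, and an index date or minimum enrolment period is commonly left to a statistical analysis plan, which is not at hand. The programme had also run since 2012, so 2019 joiners may be few. Part of this stands: the size of the bias is unknown, and the plan may yet restrict the cohort. It does not remove the point. If 2019 dates only residence, participation has no date at all and joiners are still admitted. The protocol itself names the identification year and the baseline year, and they coincide.

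A reader might infer more than the documents support:

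- **That people who left cannot be identified.** The list in section 5e says what the indicators include and need not be complete. The Background notes that HHs bill for care management, so leavers can be found from claims.
- **That keeping leavers is an error.** A group held fixed through 2020 is a defensible estimand, provided that it is stated.
- **That matching uses 2019 utilization.** No look-back window is given. Moving it before 2019 would not give HH-free values either, because established members were already enrolled.
- **That neither the sign nor the size of the estimate can be attributed to HHs.** Turnover is not stated, and a reversal of sign would depend on the relative sizes of b and d, which are also unknown.

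Aim 4 is also worded more broadly than buffering, as the impact of enrolment before and during the pandemic. The difference-in-differences contrast and the stated hypothesis, however, are about the change.

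**Conclusion.** The point holds for patients who joined during 2019. As written, Aim 4 admits them and counts their unexposed months as HH baseline, so the estimate is b + (j/2)d and not b when nobody leaves. At assumed joining shares of 0.2 to 0.3 the addition is 0.10d to 0.15d. This rests on even joining, additive and immediate effects, and parallel trends. Any rise in utilization before enrolment would come on top and is not quantified. The actual size cannot be derived from the protocol. This is a design weakness that should be corrected, not a showing that the Aim 4 result would be uninterpretable.

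**What to change.** In the main Aim 4 contrast:

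1. Define the HH group as patients who joined before 1 January 2019, using the joining date already listed, and who were still enrolled at a stated date just before the pandemic period, established from HH claims. Because follow-up starts in January 2020, 31 December 2019 would serve.
2. Define the comparison group as HH-eligible patients with no HH enrolment in 2019 who are in Medicaid on that same date.
3. Analyse patients who joined during 2019 as a separate group.
4. Hold both groups as classified through 2020 and state this as the estimand, noting that people who leave in 2020 dilute it. Add a sensitivity analysis limited to those still enrolled.

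Activity 4 uses retrospective claims, so no recruitment or data collection changes; the work is one cohort definition and one enrolment check from claims. The price is fewer HH patients in the main contrast and a result that applies to established, retained members. The Medicaid condition on the comparison group matches that retention only in part.

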## 2) Background

### Diabetes Prevalence

Type II diabetes mellitus is a common chronic disease, with an overall prevalence of 9.3% in the US (1). In New York City (NYC), the overall prevalence of diabetes is somewhat higher, 10.8%; and, the prevalence of diabetes are higher among racial and ethnic minorities, compared to Whites (2): among Hispanics, the prevalence is 15.2%; among non-Hispanic Blacks 12.8%; and, among non-Hispanic Whites 7.1%. (3) The prevalence of diabetes also is higher among those of lower socioeconomic status (SES),

compared to those of higher SES: among those living at <100% of the Federal Poverty Level (FPL) the prevalence is 14.8%; and, among the highest income group (>/=600% FPL) 4.7%.(3)

### **Diabetes Complications**

The complications of diabetes impact health and well-being. In addition to the direct metabolic consequences, diabetes increases the long-term risk of cardio-renal diseases, including coronary heart disease, stroke, heart failure, renal disease, retinopathy and blindness; and these complications contribute to health disparities. In NYC, mortality related to diabetes is significantly higher among non-Hispanic Blacks and Hispanics and among individuals living in high-poverty neighborhoods, compared to non-Hispanic Whites and those living in low-poverty neighborhoods respectively.(4) Individuals living in high-poverty neighborhoods also have higher rates of hospitalizations for diabetes-related complications.(5)

### **Diabetes care**

In order to improve health care and outcomes, reduce costs, and address health disparities related to diabetes, a number of health care interventions have been implemented by health systems and insurance providers, many focused on care management and care coordination. Increasingly, as health systems are incentivized to address health on a population level, interventions are also designed to address health determinants outside of the health care system, such as social and environmental factors and health behavior, through collaboration with community-based organizations (CBOs). Prior research among racially and ethnically diverse populations has shown that care management interventions delivered by primary care providers, registered nurses, community health workers, and endocrinologists can improve intermediate outcomes, such as hemoglobin A1c (HbA1c).(6-9) However, evidence does not presently exist on the long-term outcomes of care management and care coordination for patients with diabetes. Peek et al. describe many interventions that involve community-health system partnerships. Examples include clinics working with community-health workers, physician-referrals to community-based education, food “prescription” programs, and the integration of community-based resources into broad quality improvement initiatives.(10) While evaluations of some of these have shown promising effects on intermediate outcomes, there is little data about the overall effects of such interventions to date, especially in large, diverse, urban settings.

### **Medical homes**

Care management and community-health system partnerships commonly exist within the patient-centered medical home (PCMH) model. The Agency for Healthcare Research and Quality (AHRQ) defines the PCMH as a model of care that offers comprehensive care of each patient’s physical and mental health through a team of providers, is patient-centered, coordinates care across the health system, provides accessible services, and engages in continual quality and safety improvement evaluation and activities.(11) Consensus principles of the PCMH, building on the backdrop of 40 years of primary-care practice redesign, were established in 2007 by the American College of Physicians, the American Academy of Family Physicians, the American Academy of Pediatrics, and the American Osteopathic Association.(12) A growing number of providers are part of PCMHs, serving several million patients.(13, 14) However, there are large variations in the definition, and implementation of the PCMH.(15) This variation has made it difficult to assess the impact of the PCMH on quality of care and clinical outcomes.

### **Affordable Care Act and Medicaid Health Homes**

As part of the Patient Protection and Affordable Care Act (ACA) of 2010, “health homes” were authorized for care management and coordination for individuals enrolled in Medicaid. Under the ACA, six health home services are eligible for reimbursement: comprehensive care management, care coordination and health promotion, comprehensive transitional care, patient and family support, referral to community and social support services, and use of health information technology to link services.(16) As such, the Medicaid Health Home (HH) includes interventions previously tested among individuals with diabetes. However, the payment reforms associated with these new care delivery mechanisms add another aspect to the intervention. In addition, these types of interventions are now being expanded to include a larger patient population- those eligible for HHs. In order to be included in a HH, patients need to have chronic conditions, including serious mental illness, substance use disorders, or multiple chronic diseases, including diabetes. As of November 2014, 20 states had approved plans for HHs.(17)

New York State (NYS) established a Medicaid Health Home program in 2012, with the New York State Health Home State Plan Amendment (SPA). In New York State at the end of 2014, over 5 million low-income individuals were enrolled in Medicaid, including over 3 million of NYC’s estimated 8.4 million residents.(18, 19) The State estimated in 2012 that approximately 1 million individuals would be eligible for the HH program, including 418,677 Medicaid recipients with mental health or substance use disorders, and 386,399 participants with other chronic conditions. HHs were rolled out in three phases during 2012, with Phase I in January (which included the Bronx and Kings (Brooklyn) Counties), Phase II in April (which included New York (Manhattan), Queens and Richmond (Staten Island), the remaining counties in NYC), and Phase III in July.(20) As of August 2014, 40,776 individuals were enrolled in NYC.(21, 22) Around 35,000 Medicaid enrollees across NYS were part of precursor care management programs (including the Office of Mental Health’s Targeted Case Management Program (for those with severe mental illness), Managed Addiction Treatment Services Program, and the Comprehensive Medicaid Case Management Program (for people living with HIV/AIDS), which are all in the process of converting to HHs.(16)

The identification of individuals eligible for HHs is initiated by one of two processes: a NYS Department of Health (DOH) predictive algorithm utilizing Medicaid services data, which prioritizes individuals based on risk of future hospitalization; and community or “bottom up” referrals from healthcare providers, community-based care management providers, including harm reduction providers, and other agencies such as those who serve individuals re-entering the community from jail or prison. Enrollment in HHs has been slower than expected, and several challenges have been identified and are being addressed by the NYS DOH. These include inaccuracies in the lists of targeted individuals, challenges in the recruitment process, and individuals electing not to participate in the program.(16) The new program may put stress on already under-resourced facilities, by increasing the complexity of billing, the requirements around health information technology (HIT), the caseloads of facilities and case managers, and, in some cases, lowering reimbursement for care management services. Another significant change brought about by HHs is the expanded scope of health conditions of clients served by care management agencies that formerly provided case management for people living with HIV/AIDS, substance use disorders, or serious mental illness ([name], personal communication, March 9, 2015).

